• Describe the study, providing detail regarding the study intervention (drug, device, physical procedures, manipulation of the subject or the subject's environment, etc.). Discuss justifications for placebo control, discontinuation or delay of standard therapies, and washout periods if applicable. Identify procedures, tests and interventions performed exclusively for research purposes or more

frequently than standard of care. Include alternative therapies, concurrent therapies discontinued per protocol, risk benefit ratio, and use of tissue/specimens. Discuss monitoring during washout periods if applicable. Include brief description of follow-up, if any.

The entire study (Aims 1-3) will enroll up to 60 participants. While we anticipate that the screening blood draw will yield a number of screen failures, we expect that approximately 20-25 subjects will complete AIM-2 and 15-20 will complete AIM-3 of the study protocol. All study visits and procedures will take place in the Human Physiology Testing Core shared resource facilities located at the Duke Center for Living campus.

AIM-2

Approximately 20-25 healthy subjects will complete Aim-2 of the study and these participants will have three study visits – a baseline consent visit, and two infusion procedures.

Visit 1: The consent visit will take place at the Duke Center for Living and will last approximately two hours. If the participant has given prior verbal consent during the phone screening process, they will fast (nothing but water) for 12 hours before this visit and their body mass index (composed of weight and height measures) will be checked to see if it falls within the inclusion range. Daily medications may be taken. We will explain the study and the consent form in detail. Upon signing the consent form, a sample of blood (one teaspoon) will be drawn to measure hemoglobin A1c (HbA1c), fasting glucose level, kidney function (i.e. eGFR) and blood count (i.e. hematocrit) are within normal limits to ensure that the participant meets inclusion criteria. If these values are within the range listed below for the appropriate cohort, the participant will be scheduled for Visit 2.

If a woman is of childbearing potential, a blood (using one teaspoon of blood drawn by a needle-stick) pregnancy test will be conducted and it must be negative prior to continuation in this study.

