Subjects will have two intravenous catheters placed, one in each arm: 1) for blood drawing, and 2) for the infusion of test materials. The arm for blood draws will be heated to maintain blood flow and arterialize venous blood. Four (4.0 ml) fasting blood samples will be taken at -15, -10, -5 and 0 minutes and then a variable infusion of 20% dextrose will begin to clamp the blood glucose at basal +3 mM for 120 minutes. This hyperglycemic clamp will be stabilized over 60 minutes and 4.0 ml blood samples will be taken every 5-10 minutes during this period to establish baseline insulin secretion and active GLP-1 levels. During these visits, participants will receive an infusion of Exendin-9 (750 pmol/kg/min) between the 60 and 120 minute time-points of the clamp procedure. For consistency, blood draws (4.0 ml) will occur every 5-10 minutes between the 60 and 120 minute time-points of both visit 2 and 3. Upon completion of the final 60-minute interval for the Ex-9 infusion, both the infusion and clamp procedures will be complete. One additional blood sample (1 ml) will be drawn post the assessment to be tested immediately with the YSI glucose analyzer to ensure glucose levels are within normal limits. **Visit 3** will occur at least one week later and will be a repeat infusion procedure identical to **Visit 2**. The total amount of blood collected during each of these visits will be a maximum of ~141 ml (~9.5 Tbsp).

We will aim to complete studies in 10-15 subjects before and after approximately one week of dexamethasone(Dex) treatment to induce insulin resistance. Insulin resistance in response to a short-course (4 mg daily) of supraphysiologic glucocorticoids is an established research procedure and is completely reversible over the course of exposure we are proposing. However, the rate of reversal is variable among subjects preventing a straight counter-balanced allocation to treatment (i.e. half of subjects getting Dex before the first study and half before the second). Therefore we will enroll 6-10 subjects as controls for effects of time and repeat testing. These individuals will have identical clamps with no dexamethasone at approximately 1 week intervals and will be determined at random by study staff.

AIM-3

Approximately 15-20 subjects will complete AIM-3 of the study and these participants will have two study visits – a baseline consent visit, and one infusion procedures.

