Subjects will have two intravenous catheters placed, one in each arm: 1) for blood drawing, and 2) for the infusion of test materials. The arm for blood draws will be heated to maintain blood flow and arterialize venous blood. Four (4.0 ml) fasting blood samples will be taken at -15, -10, -5 and 0 minutes and then a variable infusion of 20% dextrose will begin to clamp the blood glucose at basal +3 mM for 120 minutes. This hyperglycemic clamp will be stabilized over 60 minutes and 4.0 ml blood samples will be taken every 5-10 minutes during this period to establish baseline insulin secretion and active GLP-1 levels. During these visits, participants will receive an infusion of Exendin-9 (750 pmol/kg/min) between the 60 and 120 minute time-points of the clamp procedure. For consistency, blood draws (4.0 ml) will occur every 5-10 minutes between the 60 and 120 minute time-points. Upon completion of the final 60-minute interval for the Ex-9 infusion, both the infusion and clamp procedures will be complete. One additional blood sample (1 ml) will be drawn post the assessment to be tested immediately with the YSI glucose analyzer to ensure glucose levels are within normal limits. The total amount of blood collected during this visit will be a maximum of ~141 ml (~9.5 Tbsp).

Selection of Subjects

• List inclusion/exclusion criteria and how subjects will be identified.

AIM-2 SELECTION OF HEALTHY SUBJECTS: Study recruitment will occur primarily through advertisements via Duke websites, as well as local newspapers (e.g. Independent, Durham Herald, Duke Chronicle); and social media venues (e.g. DMPI Facebook page, Instagram), will be used as well as use of our Duke Health and Exercise Research Trials registry. Study recruitment will also take place at public venues (e.g. Duke Farmer's Market or Community Health Fairs). Potential subjects for this study will be directed to contact the study staff to obtain more information about the study, if interested. Study participants will also be recruited using flyers posted across the Durham VAMC hospital and Duke hospital /clinic facilities, inviting interested individuals to contact the study recruitment coordinator for additional information.

Inclusion criteria:

- Healthy adults age 20-45 years
- Male or female
- Body Mass Index (BMI) ≤ 35.0 kg/m²
- HbA1c ≤ 5.7%

Ability to speak and understand English

Exclusion criteria:

- Uncontrolled high blood pressure

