- Diabetes or use of diabetes medications such as insulin or metformin
- Evidence of active heart disease or heart failure
- Lung disease or COPD
- Malabsorptive GI disease, such as celiac disease, or gastric bypass
- Significant hepatic disease
- Kidney disease or renal insufficiency (eGFR < 60 mL/kg/min)
- Untreated anemia (hematocrit < 34%) as measured at screening visit
- Pregnant females
- Active substance abuse
- Chronic use of oral steroid medications such as prednisone and hydrocortisone
- Apparent sensitivity to any of the study peptides as determined by the skin test
- Diagnosis or h/o PTSD
- · Active mental health disorders such as depression, or as a result of Traumatic Brain Injury (TBI)

Exclusion criteria will primarily be identified by way of a phone screen process conducted by the coordinator, however medical record review may be used to confirm the absence of a diabetes mellitus diagnosis or other medical conditions listed as exclusion criteria.

AIM-3 SELECTION OF SUBJECTS:

Selection of Non-Diabetic Subjects: Study recruitment will occur primarily through advertisements via Duke websites, as well as local newspapers (e.g. Independent, Durham Herald, Duke Chronicle); and social media venues (e.g. DMPI Facebook page, Instagram) will be used as well as use of our Duke Health and Exercise Research Trials registry. Study recruitment will also take place at public venues (e.g. Duke Farmer's Market or Community Health Fairs). Potential subjects for this study will be directed to contact the study staff to obtain more information about the study, if interested.

Study participants will also be recruited using flyers posted across the Durham VAMC hospital and Duke hospital/clinic facilities, inviting interested individuals to contact the study recruitment coordinator for more information. In addition, the VA Informatics and Computing Infrastructure (VINCI) will be used to identify potential subjects that meet the inclusion criteria. The study staff will pre-screen subjects listed on the VINCI reports in CPRS and contact those subjects identified to meet the inclusion criteria. Recruitment may occur through the VA Endocrinology practice and primary care clinics.

Inclusion criteria - Non-Diabetic Subjects:

- Adults age 18-65 years
- Male or female
- Body Mass Index (BMI) 25-40 kg/m²
- HbA1c \leq 6.5% as measured at screening visit
- No Diabetes or use of diabetes medications such as insulin or metformin
- Ability to speak and understand English

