- The risks from infusion of micromolar amounts of exendin-(9-39) are remote. In rare cases, nausea and vomiting have been reported as possible side effects for Ex-9. The IND has been obtained from the FDA for the infusion of exendin-(9-39) [#65837] into humans. The Principal Investigator for the present study has used this peptide in several previous studies, in doses similar to those described in this application, with no attributable adverse effects observed. Allergic reactions to synthetic peptides are possible; therefore skin testing will be performed on each subject to assess sensitivity prior to undergoing any clamp procedures. All peptides will be synthesized to GMP standards and documented sterile and pyrogen free.
- The maximum amount of blood to be withdrawn during any one of these infusion procedures is approximately 141 ml and does not constitute an undue risk in persons with normal hematocrits.
- At study entry, women of child-bearing potential will have a serum pregnancy test. The pregnancy test must be negative before the subject can undergo any study testing.
- AIM-2: Some side effects of dexamethasone may include upset stomach, headache, dizziness, insomnia, restlessness, increased appetite or weight gain may occur.

This is not a complete list of possible side effects. If the participant notices other effects not listed above, they will be advised to contact the study physician.

Costs to the Subject

• Describe and justify any costs that the subject will incur as a result of participation; ordinarily, subjects should not be expected to pay for research without receiving direct benefit.

There will be no costs to participants for any of the treatments or testing done as part of this research study. Immediate necessary care is available if an individual is injured because of participation in a research project. However, there is no provision for free medical care or for monetary compensation for such injury. During this study, hospitalizations or additional care beyond the scope of this study will be the responsibility of patients and/or their insurance company.

Data Analysis & Statistical Considerations

Describe endpoints and power calculations. Provide a detailed description of how study data will be
analyzed, including statistical methods used, and how ineligible subjects will be handled and which
subjects will be included for analysis. Include planned sample size justification. Provide estimated time

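### Pregnancy is an exclusion in Aims 2 and 3, but the one test described is at study entry and is not repeated before the infusions or the dexamethasone course

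*Combined protocol and SAP*

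**What the plan says.** Both exclusion lists under Selection of Subjects (Aim 2, and Aim 3 for all subjects) contain the entry "Pregnant females". Both aims admit women as well as men. The age criterion is "Healthy adults age 20-45 years" in Aim 2 and "Adults age 18-65 years" in both Aim 3 cohorts.

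The test is described in three places, and all three refer to the same occasion:

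- Design & Procedures, Aim 2, Visit 1: for women who could become pregnant, a blood "pregnancy test will be conducted and it must be negative prior to continuation in this study".
- Design & Procedures, Aim 3, Visit 1: the same sentence.
- Risk/Benefit Assessment: "At study entry, women of child-bearing potential will have a serum pregnancy test", followed by "The pregnancy test must be negative before the subject can undergo any study testing".

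On timing, the Aim 2 Visit 1 text says only: "If these values are within the range listed below for the appropriate cohort, the participant will be scheduled for Visit 2". Visit 3 "will occur at least one week later and will be a repeat infusion procedure identical to" Visit 2. The same section describes a dexamethasone course of about one week between the two clamps in the active arm, and clamps about one week apart in the controls.

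The Visit 2 and Visit 3 procedures cover fasting, body weight, the Ex-9 skin test (Visit 2 only), catheters, the clamp, the Ex-9 infusion and blood sampling. They include no pregnancy test or pregnancy query.

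**The concern.** Pregnancy status can change between screening and exposure. An exclusion checked by test only at entry protects participants at later visits only if the result is still current, and the protocol sets no age beyond which it is not. A site could follow every line and still give Ex-9, or start dexamethasone, on an out-of-date result.

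The exposures are an investigational peptide given under an IND and, in one arm of Aim 2, a glucocorticoid course that the protocol itself describes as above physiological levels. The Risk/Benefit Assessment states that participants gain no benefit from the study, and the template for that section asks how risks will be minimized. What is at stake is participant safety and the integrity of an eligibility rule, not the statistical analysis.

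**Working it through.** The plan gives no figure to reproduce here. The check sets the stated intervals side by side and works out how old the test result is at each exposure.

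**Inputs**

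- Test date: Visit 1 (Design & Procedures, both aims; Risk/Benefit Assessment).
- Visit 1 to Visit 2: t days. No value and no maximum are stated.
- Visit 2 to Visit 3 (Aim 2): at least 7 days. About 7 days is planned for controls, and a dexamethasone course of about 7 days lies between the active-arm clamps.
- Planned numbers: 10-15 in the dexamethasone arm, 6-10 controls, and 15-20 completers in Aim 3.

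**Age of the result at each exposure, as the plan stands**

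| Exposure | Who | Age of result |
|---|---|---|
| First Ex-9 infusion (Visit 2) | Aim 2, both arms; Aim 3 | t |
| Start of dexamethasone (after Visit 2) | Aim 2 dexamethasone arm | at least t |
| Second Ex-9 infusion (Visit 3) | Aim 2, both arms | at least t + 7 |

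Even with t = 0, the result is at least 7 days old at Visit 3. The documents give no value for t, so the following are assumptions for illustration only:

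- t = 7: at least 7 + 7 = 14 days old at Visit 3
- t = 28: at least 28 + 7 = 35 days
- t = 90: at least 90 + 7 = 97 days

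**Exposures covered by one result**

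- Dexamethasone arm: 2 infusions + 1 dexamethasone course = 3
- Controls: 2 infusions = 2
- Aim 3: 1 infusion = 1

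**Comparison within the protocol**

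Peptide sensitivity, another exclusion, is tested at Visit 2 before the infusion, and the text says explicitly that no retest is needed at Visit 3. For pregnancy the protocol states neither how long a result remains valid nor whether it must be repeated.

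**After the fix**

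The result would be 0 days old at each infusion. At the start of dexamethasone its age would be the gap from Visit 2 to the first dose. The protocol does not state that gap.

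**The case against.** The strongest reply is that the criterion is enforced. A negative result is a condition of continuing in the study and of any study testing, so nobody is exposed without one. That stands, and a reader who inferred that the exclusion goes unenforced would be wrong. But a single result of any age satisfies the condition, so the reply does not settle whether the result is current.

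A second reply is that the schedule is short. For the interval between clamps this largely stands. The stated minimum for Visit 3 has no matching maximum, and a reader might infer an open-ended gap, but the same section plans about one week between control clamps and about one week of dexamethasone between active-arm clamps. Only the interval from Visit 1 to Visit 2 has no stated timing at all, and nothing in the documents suggests that it would in fact be long.

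Third, the blood test is not the only safeguard. Exclusions are identified mainly by phone screen, medical records may be reviewed, and Data & Safety Monitoring refers to frequent contact with subjects. This is fair, but the first two are screening steps and none is described as a pregnancy check at an infusion visit.

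Fourth, a reader might infer that the study has no contraception requirement. That cannot be concluded: consent pages were removed from the file and may contain such wording. Nor do the documents support an inference that early pregnancy would distort insulin secretion between the two clamps. They also describe the risks of Ex-9 as remote and quantify no fetal risk for either agent.

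**Conclusion.** The point holds as a gap in re-verification. Pregnancy is excluded in both aims and tested once at entry, and the protocol text supplied neither limits the age of that result at Visit 2 nor repeats the test at the infusion visits. At the second Aim 2 infusion the result is at least 7 days old, plus the unstated Visit 1 to Visit 2 interval.

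The full set of three later exposures applies only to the dexamethasone arm. The number of women who could become pregnant is not stated, so no risk can be quantified. The conclusion assumes that the three descriptions refer to one test and that no repeat is specified in material removed from the file. The matter deserves correction because the remedy is simple and the exposure avoidable. It has no bearing on power, alpha, sample size or the planned analyses.

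**What to change.** Reconcile the Visit 1 and infusion-visit text under Design & Procedures, and the pregnancy-test entry in the Risk/Benefit Assessment, with the exclusion under Selection of Subjects. Keep the Visit 1 serum test for screening. Add a repeat pregnancy test, required to be negative, at each infusion visit already scheduled: Visits 2 and 3 in Aim 2 and Visit 2 in Aim 3. State that the Aim 2 Visit 2 result must also precede the dexamethasone course. This re-checks an existing eligibility criterion and proposes no dose, schedule or stopping rule.

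The cost is one kit per infusion visit for each woman who could become pregnant, short text edits, and an occasional exclusion later than screening. At the planned upper numbers of completers (25 in Aim 2, 20 in Aim 3), the ceiling is 2 × 25 + 20 = 70 tests even if every completer needed them; participants who start but do not complete could add a few. Repeat testing reduces exposure in very early pregnancy but cannot eliminate it, because a conception too recent to detect would still be missed.

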Visits 2 and 3: Each participant will have two 4-hour hyperglycemic clamp procedures with the addition of the GLP-1 receptor antagonist Exendin-9 (Ex-9) to determine the *fasting GLP-1 effect*. During both visits, the participants will receive an infusion of Ex-9 beginning at the 60-minute mark of the clamp procedure; this will allow a comparison of glucose-stimulated insulin secretion with and without GLP-1 action, a parameter we have termed the *fasting GLP-1 effect*. Throughout the glucose infusions during visits 2 and 3, 1 ml blood samples will be taken every 5-10 minutes beginning at the -15 minute time-point and continue until the end of the 120 minute procedure. These samples will be tested immediately with a YSI glucose analyzer and the values used to adjust the glucose infusion rate to maintain stable blood glucose concentrations (a glucose clamp) throughout the experiment.

Subjects will report to the Duke Center for Living after a 12-hour fast. Study staff will obtain the participant's current body weight. At Visit-2 a skin test to confirm they do not have any sensitivity to the Ex-9 investigational compound that will be used during both visits 2 and 3 will be administered. The skin test is specified by the FDA as a precaution for immediate hypersensitivity; 5 ng of Ex-9 is injected intradermally and subjects are monitored for 30 minutes for a wheal/flare reaction. This skin test must be negative in order to continue with the study testing. Once a negative skin test has been recorded, the participant will not need to be retested for sensitivity to Ex-9 at visit 3.

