to target accrual and accrual rate. Describe interim analysis including plans to stop accrual during
monitoring. Phase I studies, include dose escalation schema and criteria for dose escalation with
definition of MTD and DLT.

AIM-2 – The primary outcome for visits 2-3 will be to measure the effects of Ex-9 on fasting glucose-stimulated insulin secretion before and after experimentally induced insulin resistance. The primary experimental variable for analysis will be C-peptide during the clamp. Mean values will be compared between the period of glucose only stimulation and glucose with Ex-9. For each subject in the active treatment arm data will be analyzed using 2-way ANOVA for repeated measures using time (0-60 vs 60-120 min) and treatment (Dex vs no Dex) as the two factors. Based on our previous studies we expect a significant time effect due to Ex-9. If there is an interaction with treatment we would conclude that experimental insulin resistance influences the *fasting GLP-1 effect*. Data from control subjects will be analyzed identically; here we expect no interaction, indicating that the fasting GLP-1 is a stable measure. In our previous study using Ex-9 during a glucose clamp, the average coefficient of variation in insulin concentrations at the conclusion of each step in the ramp was 30%. Using this estimate of between subject variation, detecting a 20% difference between subsequent steps in the GLP-1 ramp with a power of 80% and significance level of 0.05 will require 8 subjects.

AIM-3 – The primary outcome measure for this study will be the fasting GLP-1 effect. This will be defined as the difference in steady state glucose-stimulated insulin secretion with and without Ex-9. The difference will be expressed as a percentage of glucose stimulated insulin secretion without Ex-9, and serve as the primary variable for comparison among the lean, obese and diabetes cohorts.

Data & Safety Monitoring

Summarize safety concerns, and describe the methods to monitor research subjects and their data to
ensure their safety, including who will monitor the data, and the frequency of such monitoring. If a
data monitoring committee will be used, describe its operation, including stopping rules and frequency
of review, and if it is independent of the sponsor (per 45 CFR 46.111(a) (6)).

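### Aim 2 analyses whole-hour mean C-peptide as if it were insulin secretion, so both windows contain transition periods that can shrink, cancel or reverse the Dex contrast

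*Combined protocol and SAP*

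**What the plan says.** In Data Analysis & Statistical Considerations, AIM-2 (repeated in the Research Abstract), the aim is "to measure the effects of Ex-9 on fasting glucose-stimulated insulin secretion before and after experimentally induced insulin resistance". The outcome is a concentration: "The primary experimental variable for analysis will be C-peptide during the clamp". It is summarised by period: "Mean values will be compared between the period of glucose only stimulation and glucose with Ex-9". The repeated-measures ANOVA is specified as "using time (0-60 vs 60-120 min) and treatment (Dex vs no Dex) as the two factors", and an interaction is to be read as an influence of insulin resistance on the fasting GLP-1 effect.

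Design & Procedures, AIM-2, Visits 2 and 3, gives the timing. Dextrose starts from the fasting state at minute 0, and "This hyperglycemic clamp will be stabilized over 60 minutes". Then "participants will receive an infusion of Exendin-9 (750 pmol/kg/min) between the 60 and 120 minute time-points of the clamp procedure". The Ex-9 window therefore opens at the minute the infusion starts. Sampling is dense: "blood draws (4.0 ml) will occur every 5-10 minutes between the 60 and 120 minute time-points", with the same spacing in the first hour.

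The plan states no lag, late sub-window, end-of-period value or conversion of C-peptide to a secretion rate. By contrast, Aim 3 defines the fasting GLP-1 effect on steady-state secretion, and the 30% coefficient of variation quoted for Aim 2 comes from values at the end of each step of a ramp.

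**The concern.** A plasma concentration reflects earlier secretion until that material has cleared. If secretion steps up at minute 0, C-peptide climbs through the first hour. If secretion steps down at minute 60, C-peptide made before Ex-9 is still circulating in the second hour. The first mean therefore understates glucose-stimulated secretion without Ex-9, and the second overstates secretion with Ex-9. Both errors push the contrast the same way, against showing a fall.

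The Aim 2 conclusion rests on the difference between two such contrasts, one per visit, in 10-15 Dex subjects. Dex is given to induce insulin resistance, so secretion may well differ between visits. In that case the build-up term does not subtract out. The 6-10 no-Dex controls cannot remove it, because they have no Dex-induced change in level. A real change in the fasting GLP-1 effect could be missed or read in the wrong direction.

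**Working it through.** The plan gives no figure for this contrast to reproduce. Its sample size of 8 concerns insulin at successive steps of a GLP-1 ramp and is not used here.

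**Inputs from the documents:** windows 0-60 and 60-120 min; glucose from minute 0; Ex-9 from minute 60.

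**Assumptions:** one-compartment clearance with half-life h, the same at both visits, k = ln 2 / h. Secretion steps at once from basal S0 to stimulated S1 at minute 0, and to (1 - f)S1 at minute 60. C-peptide is in units of the secretion it would reflect at steady state.

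**Step 1: carry-over in the Ex-9 hour.** Share of the fall missing from the 60-120 min mean: L = (1 - e^(-60k)) / (60k). For h = 30, 60k = 1.386 and L = 0.75 / 1.386 = 0.541.

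| h (min) | missing (L) | seen (1 - L) |
|---|---|---|
| 10 | 24% | 76% |
| 15 | 34% | 66% |
| 20 | 42% | 58% |
| 30 | 54% | 46% |
| 35 | 59% | 41% |

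Two-exponential clearance (assumed fast half-life 4-6 min, slow 30-36 min) gives 37-48% missing. Any delay before Ex-9 reaches full effect adds to the loss.

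**Step 2: the contrast as planned, with the first hour included.** With e = e^(-60k):

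- mean 0-60 = S1 - (S1 - S0)L
- mean 60-120 = (1 - f)S1 + [f S1 - (S1 - S0)e]L
- difference D = -f S1(1 - L) + (S1 - S0)L(1 - e)

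Take h = 30, S0 = 0.5, S1 = 1, f = 0.2. Then D = -0.2 × 0.459 + 0.5 × 0.541 × 0.75 = -0.092 + 0.203 = +0.111. The 0-60 mean is 1 - 0.5 × 0.541 = 0.73, so a true 20% fall appears as a rise of 0.111 / 0.73 = 15%. With no fall at all, D = +0.203.

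**Step 3: the time by Dex interaction.**

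*Equal basal and stimulated levels at both visits, fall deepening from 20% to 30%.* The build-up terms subtract out, leaving -0.10 × (1 - L) = -0.058, -0.046 and -0.041 at h = 20, 30 and 35, against a true -0.10. Here the contrast does shrink by L.

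*Dex doubles secretion (S0 = 1, S1 = 2) and the fall deepens from 20% to 30%.* True interaction: -0.3 × 2 + 0.2 × 1 = -0.40. Planned interaction: -0.40(1 - L) + 0.5 L(1 - e). At h = 30 this is -0.184 + 0.203 = +0.02. Across half-lives:

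| h (min) | planned (true -0.40) |
|---|---|
| 10 | -0.19 |
| 15 | -0.11 |
| 20 | -0.05 |
| 30 | +0.02 |
| 35 | +0.04 |

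**Step 4: late-window C-peptide, 40-60 vs 100-120 min.** L is replaced by M = (e^(-40k) - e^(-60k)) / (20k) = 0.18, 0.32 and 0.37 at h = 20, 30 and 35. In the Dex-doubling example at h = 30 (M = 0.318): -0.40 × 0.682 + 0.5 × 0.318 × 0.75 = -0.273 + 0.119 = -0.15. The sign is restored, but well under half of -0.40 is recovered. A correctly deconvolved rate recovers -0.40 in this model.

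**The case against.** **The size is not in the documents.** They state no C-peptide half-life or clearance. This stands, so every percentage above is conditional, and with fast clearance the loss is nearer a quarter to a third.

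**A constant dilution would be harmless to direction.** If both visits were diluted by the same factor, a zero interaction would stay zero and the sign would be kept, and the planned conclusion is qualitative. This is right only when C-peptide is already level in the first hour, or the build-up is the same at both visits. Dextrose starts from fasting at minute 0 and the first hour is described as stabilisation, so the plan does not secure the first condition. A Dex effect on secretion would break the second.

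**The sign change depends on scale.** In the Dex-doubling example at 30 min, expressing each contrast as a percentage of its own 0-60 mean gives +15% without Dex and 0.130 / 1.459 = +9% with Dex. That is about -6 points against a true -10, so the direction survives. But the Aim 2 text compares means and states no percentage or log scale, and this rescue relies on the basal-to-stimulated ratio being equal at both visits.

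**Loss of power is not calculated.** This stands. No C-peptide standard deviation is given, and true between-subject variation in the effect would shrink too.

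**The remedy may not be free.** The text says the frequent draws serve to establish insulin secretion and active GLP-1. It does not say that every sample is assayed for C-peptide. This also stands and is carried into the cost.

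**Conclusion.** The point holds. The Aim 2 variable is not the quantity in the objective, and as written both hourly means include periods when C-peptide has not caught up with secretion. Some distortion follows at any finite clearance rate; only its size rests on assumptions. For assumed one-compartment half-lives of 20-35 min, the Ex-9 hour alone misses about 42-59% of a step fall, and 24-34% at 10-15 min.

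A reader might infer that a fixed half of both the Ex-9 effect and the Dex contrast is lost, for example that a 20-point Dex difference would show as about 9. The documents do not support that. They give no half-life, and the halving of the Dex contrast needs a first hour that is already level, or equal basal and stimulated levels at both visits. Otherwise the build-up in 0-60 min enters the same contrast, and the interaction on the raw scale can be cancelled or change sign. The -0.40 against +0.02 result illustrates this under its stated assumptions and is not a forecast.

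**What to change.** Make the Aim 2 primary variable a pre-specified insulin secretion rate, deconvolved from C-peptide in the samples drawn every 5-10 minutes with named population kinetic parameters. Compare a late window of each hour, for example 40-60 vs 100-120 min, in line with Aim 3's steady-state definition. State whether the Aim 2 contrast is absolute or a percentage. Keep whole-hour mean C-peptide as a supportive analysis.

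If deconvolution is not adopted, use late-window C-peptide in both hours, and say that it still misses about 18-37% of the fall at assumed half-lives of 20-35 min and does not fully remove the build-up.

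Cost: analysis wording, a deconvolution step, reliance on population kinetic parameters, some added noise, and C-peptide assay of samples already drawn if not all are assayed now. No extra visits, subjects or blood draws.
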